2.7 What is the proposed duration of follow-up?

Patient clinical status will be monitored daily during the acute care unit stay for up to 3 days after termination of study IP (maximum 7 days). Hospital outcomes will be abstracted from the chart once the patient is discharged.

2.8 and 2.9 What are the proposed primary and secondary outcome measures?

The primary outcome for this phase III trial is persistent organ dysfunction (POD)+death at 28 days, a novel composite endpoint that combines being alive and being free of organ support (inotropes or vasopressors or mechanical circulatory assistance, renal replacement therapy and mechanical ventilation).⁷⁷

The most important secondary endpoint of this trial will be “time to discharge alive from hospital.” The other secondary outcomes will be the components of 28-day POD which include mortality, use of inotropes or vasopressors or mechanical circulatory assistance, renal replacement therapy and mechanical ventilation and POD-free days in the first 28 days.

Tertiary outcomes will include intensive care unit (ICU) outcomes (e.g. length of stay, duration of mechanical ventilation, and readmission rates); hospital outcomes (hospital mortality, length of stay, bacteremia with gram-negative bacilli, and readmission rates); and 6-month outcomes (mortality, health related quality of life and physical function domain of the Short Form-36 (SF-36) questionnaire, activities of daily living and instrumental activities of daily living). We will also record frequency of operative procedures for burn care, presence of inhalation injury, blood transfusions, and other major cost drivers to support our economic evaluation.

2.10 What is the proposed sample size and what is the justification for the assumptions underlying the power calculation?

The primary outcome for this trial is PODS+death at 28 days after randomization. Based on estimates from currently available pooled data from the RE-ENERGIZE study with $\geq 20\%$ TBSA (n=539), we estimate that the 28-day PODS rate will be 27%. Based on our simulations accounting for two interim analyses (see Tables in Appendix C), we estimate that with 333 subjects per arm, we would achieve 78% power to observe a reduction at a one-sided alpha of 0.025 (or two-sided alpha=0.05) if the rate of PODS at 28 days was reduced from 27% to 18% (RRR=33.3%).

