2.16 What is the statistical and data analysis plan?

In accordance with the intent-to-treat (ITT) principle, the analysis will include all patients in the arm to which they are randomized regardless of study compliance except patients who do not receive any of the study intervention (modified ITT analysis). In addition, we will conduct a per-protocol analysis of all truly eligible patients who receive all 16 doses. All of the analysis, including reporting of participant flow and patient characteristics by arm, will be presented in accordance with the CONSORT statement. Our primary outcome (alive and PODS free at 28 days) will be compared between groups using by an adjusted relative risk estimated by a modified Poisson regression with robust standard errors clustering by site and controlling for the following baseline covariates: TBSA burn, traumatic brain injury, mechanically ventilated at baseline and injury severity score.⁸⁰ This approach will meet regulatory guidance and best practices suggesting that site and strongly predictive baseline covariates be considered for adjustment in the analysis of multicenter studies.⁸¹⁻⁸³ Binary secondary outcomes will be analyzed similarly.

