Based on our substantial prior experience with this population, we expect minimal missing data for all 28-day outcomes. However, details of missing data will be provided, and for the primary outcome, we will perform a sensitivity analysis using a graphical pattern-mixture tipping-point approach demonstrating the treatment effect over the possible range of missing outcomes.^{84,85} Lengths of ICU and hospital stay will be reported by arm using the subdistribution cumulative incidence function (CIF), where death is treated as a competing risk precluding the possibility of discharge. The between-arm difference in time to live discharge will be summarized by the subdistribution hazard ratio with 95% confidence intervals and p-values estimated by the Wald test from the Cox proportional hazards model, with site as a random frailty to account for potential between-site heterogeneity and adjusting for the same baseline covariates as for the primary outcome. For this analysis, survivors will be censored at the earliest of last date known alive or 183 days after randomization. Patients who die prior to discharge will be censored after the end of the follow-up period (i.e. >183 days) to account for the competing risk of death. This will yield virtually the same results as the Fine and Gray approach treating death as a competing risk precluding discharge, except we will have incorporated ICU as a random effect. This outcome is also known as time-to-discharge-alive (TTDA). The distribution of ventilator-free days and PODS-free days up to day 28 will be compared between arms by the

empirical distribution function depicting the proportion of people (y-axis) with at least 1 through 28 free days (x-axis) by arm.

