Six-month mortality will be reported by group using Kaplan-Meier curves with between-group differences summarized by the hazard ratio and corresponding 95% confidence intervals estimated from the Cox proportional hazards model with site as a random frailty and adjusting for the same baseline covariates as the primary outcome. Survival will be censored at 183 days or time last known alive for patients lost to follow-up. Six-month health-related quality of life and physical-function status will be reported for survivors only since our tools (SF-36 and Katz's ADL index) are not defined for decedents. When interpreting these outcomes, we will only consider results definitive if they are in the same direction as survival. For example, if the intervention arm had both higher survival (regardless of statistical significance) and better SF-36, then we would conclude that health-related quality of life was improved in the intervention arm compared to the control arm. For each of these outcomes we will report the mean scores by arm and estimate the mean difference between arms with 95% confidence intervals. Estimates for these outcomes will be obtained from a linear mixed effects model with our primary predictor of interest being a fixed effect indicator for treatment arm but also including site as a random effect and the following fixed baseline covariates: age, sex, ethnicity, TBSA burn, traumatic brain injury, mechanically ventilated at baseline and injury severity. These estimates will use the augmented inverse probability to minimize bias due to missing data among survivors.⁸⁶

Although the secondary outcomes will play a mostly supportive and exploratory role, result interpretation will consider the multiplicity of tests, and the false discovery rate for correlated tests will be reported if nominal p-values reach ≤ 0.05 for any secondary outcomes.⁸⁷ Tertiary outcomes will be reported without p-values.

There will be two interim analyses for futility/harm after the primary outcome is available on 222 and 444 patients. Both interim analyses will suggest stopping for futility/harm if the adjusted RR of the PODS+death is >1.1 favoring control. The study will not stop early for benefit. Details of the operating characteristics of this study under this futility rule are provided in Appendix C.

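### POD-free days is a named secondary outcome, but its only planned comparison is a plotted distribution function, so the plan yields no summary between-arm effect with uncertainty

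*Combined protocol and SAP*

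**What the plan says.** Sections 2.8 and 2.9 define the primary outcome, POD+death at 28 days, as "a novel composite endpoint that combines being alive and being free of organ support". Their list of other secondary outcomes consists of the components of that composite and ends with "renal replacement therapy and mechanical ventilation and POD-free days in the first 28 days".

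The only analysis of POD-free days is in section 2.16, where one sentence commits to a comparison of the two arms on this outcome and on ventilator-free days. The method it names is this: "empirical distribution function depicting the proportion of people (y-axis) with at least 1 through 28 free days (x-axis) by arm".

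The same section treats its neighbours differently:

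- After the adjusted relative risk for the primary outcome it adds: "Binary secondary outcomes will be analyzed similarly".
- The arm difference in time to live discharge is to be "summarized by the subdistribution hazard ratio with 95% confidence intervals and p-values estimated by the Wald test from the Cox proportional hazards model".
- On multiplicity, "the false discovery rate for correlated tests will be reported if nominal p-values reach ≤ 0.05 for any secondary outcomes". Only tertiary outcomes are expressly reported without p-values.

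**The concern.** An empirical distribution function drawn by arm describes the data. It does not say how large the difference between arms is, or how precisely that difference is known. A trial that followed section 2.16 exactly would report two curves for a named secondary outcome, and a reader would have to judge by eye whether they differ.

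Two things are at stake. First, if the curves look different, someone will want a number, and the choice of summary (mean difference, median, rank test or odds ratio) would then be made after the data are seen. Second, section 2.10 says that a numerical advantage without significance would be called indeterminate and could be combined with other trials. Pooling any outcome needs an effect and its standard error, and a plot supplies neither.

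**Working it through.** **1. What each outcome receives under sections 2.8, 2.9 and 2.16**

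| Outcome | Tier | Between-arm summary | Uncertainty |
|---|---|---|---|
| Binary components of POD | secondary | adjusted relative risk, modified Poisson | robust standard errors |
| Time to discharge alive | secondary | subdistribution hazard ratio | 95% CI, Wald p-value |
| POD-free days | secondary | none (plot) | none |
| Six-month mortality | tertiary | hazard ratio | 95% CI |
| SF-36, ADL | tertiary | mean difference | 95% CI |

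POD-free days is a count from 0 to 28, so the rule for binary outcomes does not reach it.

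**2. The plan's own power figure for the related binary endpoint**

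Inputs from section 2.10: 27% vs 18%, 333 per arm, two-sided 0.05.

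- SE of log RR = √[0.73/(333×0.27) + 0.82/(333×0.18)] = 0.1476.
- z = |ln(0.18/0.27)|/0.1476 = 0.4055/0.1476 = 2.746.
- Power = Φ(2.746 − 1.960) = 78.4%.

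Simulation with the RR > 1.1 rule at 222 and 444 patients gives 78.7%, and under RR = 1 it stops 33.3% and 8.0% of trials at the two looks. Both agree with Appendix C, Table B (78.1%; 33.3% and 8.0%).

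**3. Would a test on POD-free days be stronger?**

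The documents give no distribution, so the following are assumptions: patients with the primary event score 0 (27% of controls); 20%, 35% or 50% of controls score 28; the rest are spread evenly over 1–27. With θ = P(T>C) + ½P(T=C) and p̄ the mean level probabilities over both arms, Wilcoxon power is Φ(|θ − ½|/√V − 1.96), where V = 666(1 − Σp̄³)/(12×333²).

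| Effect, 27% → 18% at zero | θ | Power |
|---|---|---|
| Same odds ratio along the whole scale | 0.584 / 0.579 / 0.570 | 96.7 / 95.9 / 93.5% |
| Only the share at zero falls | 0.545 | 53 / 55 / 59% |
| Patients move only from 0 to 1–14 days | 0.525 / 0.521 / 0.518 | 20 / 16 / 13% |

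The odds ratio is (0.18/0.82)/(0.27/0.73) = 0.5935. Example for the 35% case: V = 0.000460, √V = 0.0214, and 0.0793/0.0214 = 3.70, so power = Φ(1.74) = 95.9%.

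The first row is demanding. It requires the share with all 28 days free to rise from 20% to 30%, from 35% to 48%, or from 50% to 63%.

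Smaller effects show the same dependence on shape:

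| Rate at zero, treated arm | Binary log-RR test | Rank test, common odds ratio (35% case) | Rank test, only share at zero changes |
|---|---|---|---|
| 20.25% | 53% | 77% | 33–38% |
| 21.6% | 37% | 56% | 23–26% |

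**4. What an estimate would add**

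A second illustration again put 27% vs 18% at zero. It gave 10–60% of the remaining controls a score of 28 and let the others lose an exponential number of days (mean 9 in control, 7.5–9 in treatment). A mean difference then has a 95% CI half-width of about 1.6–1.8 days, for an expected difference of about 1.8–3.1 days. Wilcoxon power was 53–58% when only the share at zero changed, 73% when duration also shortened, and 94% when the share of those patients with all 28 days free also rose from 35% to 42%.

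**The case against.** The best defence is that section 2.16 gives secondary outcomes a mostly supportive and exploratory role. Formal inference goes to the primary outcome, to time to discharge alive as the most important secondary outcome, and to the binary components. Describing one lesser secondary outcome by a plot could fit that hierarchy. The curves also let a reader take off the proportion in each arm with at least k free days for every k from 1 to 28, so the plan is not silent about the outcome.

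This limits the weight of the point but does not remove it. The plan does not label POD-free days descriptive, it uses the language of comparison, and it gives intervals to outcomes that it ranks lower.

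Four stronger readings are tempting, and the documents do not support them:

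- *A test on POD-free days would be more powerful than the primary.* This holds only if the effect runs along the whole scale, and no document gives the distribution needed to say so.
- *It is the only outcome that separates early from late freedom from support.* Section 2.16 also plans ventilator-free days, and sections 2.8 and 2.9 list duration of mechanical ventilation. Both carry timing.
- *Multiplicity control is broken.* The false-discovery-rate sentence is conditional on p-values that exist. An outcome without a p-value adds no multiplicity and does not breach it.
- *The plan relies on POD-free days to interpret an indeterminate primary result.* Section 2.10 does not mention this outcome in that context.

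**Conclusion.** The point holds as a gap in specification. Followed exactly, section 2.16 produces no summary between-arm effect with uncertainty for a named secondary outcome, while it does so for the other secondary outcomes and for several tertiary ones. This rests on the text alone and needs no assumption.

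The point has no size in power. The range of 13–97% against 78% reflects assumed distributions and assumed forms of effect, so it supports neither a gain nor a loss. Those calculations also pool deaths with persistent organ dysfunction at zero, so they are not the power of the analysis proposed below, which ranks deaths lowest.

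The primary conclusion and its error control are unaffected. This is a cheap improvement to the analysis plan, not a flaw in the design.

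**What to change.** Keep the plot. In section 2.16:

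1. Define the POD-free-days score before naming any model: deaths by day 28 take the lowest rank, and a rule is stated for support that stops and restarts.
2. Pre-specify one between-arm estimate with a 95% CI. A suitable choice is a common odds ratio from a proportional-odds model, adjusted for the primary-outcome covariates (TBSA burn, traumatic brain injury, mechanical ventilation at baseline, injury severity score), with site as a random effect.
3. Name a site-stratified Wilcoxon (van Elteren) test as the check, since a common odds ratio may describe the effect only approximately.
4. Include the resulting p-value in the secondary false-discovery-rate family.

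If the sponsor intends description only, the minimum is to say so and to state that the outcome is outside that family.

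The cost is a few lines of text and one model on data already planned. The downsides are one more p-value in the family and reliance on an approximate proportional-odds summary. The primary endpoint and sample size do not change.

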Appendix B: Schedule of Assessments

SCHEDULE OF ASSESSMENTS	Screening / Baseline Day 1	Day 2	Day 3	Day 4	Day 5	Day 6	Day 7	Day 8	Ad Hoc	Outcomes (d/c to 90 days max)	6 Month Follow-Up	Early withdrawal
SCREENING/Pre-RANDOMIZATION (collected once)												
Obtain Consent												
Rule-out Pregnancy (if applicable) as SOC												
Inclusion Criteria met (age; burn size)												
Exclusion Criteria - none present												
BASELINE (collected once at beginning of study period)												
Randomization												
Demographics, Comorbidities, APACHE II Score, hospital & ACU admit date/time												
Burn Injury Assessment (date/time; type; % TBSA)												
Clinical Frailty Scale assessment												
TRAUMA (collected once at baseline)												
Traumatic Brain Injury, GCS, other trauma												
SOFA (record from ACU admission to 3 days after last dose of IP)												
PaO ₂ /FiO ₂ (lowest)												
Platelets (lowest)												
MAP (lowest)												
MICROBIOLOGY (record from >72 hours after ACU admission to ACU discharge for a maximum of 3 months)												
Gram negative bacteremias												
VENTILATION/RRT (record data from hospital admission to hospital discharge for a maximum of 3 months)												
Invasive Mechanical Ventilation												
Renal Replacement Therapy (dialysis)												

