Severe acid-base imbalance												

SCHEDULE OF ASSESSMENTS	Screening / Baseline Day 1	Day 2	Day 3	Day 4	Day 5	Day 6	Day 7	Day 8	Ad Hoc	Outcomes (d/c to 90 days max)	6 Month Follow-Up	Early withdrawal
Severe electrolyte imbalance												
Refractory hypoglycemia												
SERIOUS ADVERSE EVENTS (recorded within 24 hrs of awareness, from randomization to 3 days after the last dose of IP)												
Event description, seriousness, outcome, expectedness, relationship to IP, action taken with IP, action taken to treat event												
HOSPITAL OVERVIEW (recorded once after hospital discharge to a maximum of 3 months)												
ACU – date of discharge, death, or consent withdrawal.												
Hospital – date of discharge, death, or consent withdrawal.												
Location discharged to or cause of death.												
COVID-19 (collected once and recorded at hospital discharge, or 3 months after admission)												
COVID-19 Status, negative, positive, presumed positive, not tested/unknown and date of result or determination												
SURVIVAL ASSESSMENT (collected once at 6 months after admission (+/- 14 days))												
Alive or deceased, date, source of data.												
If data not obtained, record efforts made, and date last known to be alive.												
HEALTH RELATED QUALITY OF LIFE ASSESSMENTS (collected once at 6 months after admission (+/- 14 days))												
SF-36 questionnaire												
Katz ADL questionnaire												
Lawton IADL questionnaire												
Data Query Resolution (resolve after data entry milestones: hospital overview and survival/6-month assessments)												
Data query checks are built into the EDCS and will generate queries to address missing, inconsistent, and illogical data.												

Data Quality Management and Source Verification/Monitoring

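### The 6-month SF-36 and ADL models have no baseline outcome to adjust for and omit the Clinical Frailty Scale, the only general functional-status scale scheduled at baseline; adding it is a cheap, modest gain in precision.

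*Combined protocol and SAP*

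**What the plan says.** Section 2.16 fits a linear mixed model to the 6-month quality-of-life and physical-function scores. Treatment arm is the fixed effect of interest, site is a random effect, and the adjustment set is "the following fixed baseline covariates: age, sex, ethnicity, TBSA burn, traumatic brain injury, mechanically ventilated at baseline and injury severity". The analysis is restricted to the living: "Six-month health-related quality of life and physical-function status will be reported for survivors only". For missing questionnaires the plan says only: "These estimates will use the augmented inverse probability to minimize bias due to missing data among survivors". It lists no variables for the response model or the outcome (augmentation) model.

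Appendix B gives the timing of the instruments: "HEALTH RELATED QUALITY OF LIFE ASSESSMENTS (collected once at 6 months after admission (+/- 14 days". There is no baseline or recalled pre-burn administration. The baseline block does include "Clinical Frailty Scale assessment". The rest of that block is "Demographics, Comorbidities, APACHE II Score, hospital & ACU admit date/time", plus burn and trauma items. No analysis or subgroup text in sections 2.16 and 2.17 mentions the frailty score.

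On adjustment in general, section 2.16 cites guidance that "site and strongly predictive baseline covariates be considered for adjustment in the analysis of multicenter studies". Sections 2.8 and 2.9 class the 6-month outcomes as tertiary, and section 2.16 adds: "Tertiary outcomes will be reported without p-values". Section 2.16 names SF-36 and the Katz index as its tools. Lawton IADL appears by name only in Appendix B, and I take the same model to apply to it.

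**The concern.** With a patient-reported or functional outcome, the baseline value is usually the first covariate one would want. Here there is none, so the question is what stands in for it. The listed covariates describe demographics, the burn, associated trauma and ventilation. None describes how the patient functioned before the injury. Comorbidities and APACHE II, also collected, measure disease burden and acute severity. The frailty score is the closest available substitute, and the plan gives no reason for leaving it out, although these models already add age, sex and ethnicity to the primary-outcome set.

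What is at stake is mainly the width of the intervals. Mean differences with 95% confidence intervals, without p-values, are the whole inferential output for these outcomes. A second, smaller matter is that the augmented inverse-probability estimator relies on the variables placed in it to explain non-response, and the plan does not say what they are.

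**Working it through.** The plan gives no SD, power or precision figure for SF-36 or ADL, so there is no figure of its own to reproduce. What follows is conditional on stated assumptions.

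**Inputs from the documents**
- 333 patients per arm (section 2.10).
- No more than 10% dead by day 47 (section 2.10); 6-month mortality is not given.
- 5% loss, allowed for in the time-to-discharge calculation (section 2.10); under 4% lost at 6 months in the previous trial (sections 2.13 and 2.14). Neither is a questionnaire non-response rate.

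**Assumptions**
- 90% alive and 95% of those responding: 333 × 0.90 × 0.95 ≈ 285 per arm.
- Partial correlation r between frailty score and 6-month score, given the listed covariates, of 0.1 to 0.5.

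**Precision**

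In units of the residual SD after the listed covariates, the 95% half-width is 1.96 × √(2/n) = 1.96 × √(2/285) = 0.164. Adding a covariate with partial correlation r multiplies this by √(1 − r²). The equivalent gain in sample size is 1/(1 − r²) − 1.

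| r | Half-width (SD) | Narrower by | Equivalent extra survivors |
|---|---|---|---|
| 0 (scale omitted) | 0.164 | – | – |
| 0.1 | 0.163 | 0.5% | 1.0% |
| 0.2 | 0.161 | 2.0% | 4.2% |
| 0.3 | 0.157 | 4.6% | 9.9% |
| 0.4 | 0.151 | 8.3% | 19.0% |
| 0.5 | 0.142 | 13.4% | 33.3% |

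With 85–90% alive and 4–30% non-response, n runs from 198 to 288 per arm and the unadjusted half-width from 0.197 to 0.163 SD. The percentage narrowing does not depend on n.

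**Missing questionnaires**

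Suppose frailty is left out of the estimator altogether. If frailty-related non-response works alike in both arms, the bias in the arm difference is about zero in a linear additive model. If it occurs in one arm only, the bias is r × m/(1 − m) × d. Here m is the non-response share and d is the frailty gap, in SD, between non-responders and all survivors in that arm. With r = 0.3 and d = 1:

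- m = 4%: 0.3 × 0.04/0.96 = 0.013 SD
- m = 5%: 0.3 × 0.05/0.95 = 0.016 SD, about a tenth of the 0.164 half-width
- m = 15%: 0.3 × 0.15/0.85 = 0.053 SD, against a half-width of 0.174 (n = 255)
- m = 30%: 0.3 × 0.30/0.70 = 0.129 SD, against a half-width of 0.191 (n = 210)

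The last two lines show where the issue would begin to matter. The documents do not say that non-response will be that high.

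**The case against.** The strongest reply is that this is preference rather than error. Seven covariates plus site are prespecified, the cited guidance asks only that strong predictors be considered, and comorbidities and APACHE II are left out of this model too. The outcomes are tertiary and carry no power claim. Section 1.1 describes burns as striking mainly younger and middle-aged workers, so frailty scores may cluster at the low end and add little beyond age. At r = 0.1 the gain is negligible. All of this stands as a limit on size. It does not remove the point, because the frailty score is the nearest thing to a baseline value of these outcomes and is already scheduled.

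It is also fair to say that complete, usable scores are not assured. Section 2.3 expects most patients to be unable to consent and most families to be absent early on, so a Day 1 score may be missing or given by proxy. The documents do not say that the score refers to the pre-injury state, or that it was collected in the 180 pilot patients who are pooled into the analysis. This stands, and the fix has to cover it.

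Two stronger readings are tempting. A reader might infer that the missing-data weighting leaves frailty out. Section 2.16 does not support that, because the estimator's variables are not listed and the scale is neither included nor excluded. A reader might also infer that the omission biases the treatment comparison. Omitting a prognostic covariate does not in itself bias a randomised comparison. Restriction to survivors is a possible exception, but the documents give nothing from which to size it.

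**Conclusion.** The point holds as a modest, low-priority improvement. The documents establish three facts: these outcomes have no baseline value, a baseline functional-status scale is scheduled, and the model's covariate list omits it. The expected benefit is confidence intervals about 0.5% to 13% narrower for r between 0.1 and 0.5. At r = 0.3 the half-width falls from 0.164 to 0.157 SD, which is unlikely to change an interpretation.

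The size rests on a correlation the documents do not give and on the score describing pre-injury status. That frailty drives non-response is likewise an assumption. On missing data, the supportable finding is that the estimator is unspecified. At the quoted 4–5% loss, the bias is only about 0.013–0.016 SD even in the one-arm scenario above (r = 0.3, d = 1).

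**What to change.** In section 2.16, before unblinding:

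- Add the baseline Clinical Frailty Scale score as a fixed covariate in the 6-month SF-36, Katz ADL and Lawton IADL models.
- List the variables in the outcome and response parts of the augmented inverse-probability estimator, with the frailty score among them.
- State that the score refers to the patient's pre-injury status.
- Give a simple rule for missing scores, such as a missing indicator or single imputation of the baseline covariate, and say that it also applies to pilot patients without a score.

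The cost is a few lines of text, one degree of freedom if the score enters linearly (one more with a missing indicator), and the handling of some missing baseline values. It needs no extra patients and no new assessments. Prespecifying it now also avoids the appearance of a data-driven choice later.
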